Ultrasound Guided Peripheral IV: Boston Medical Center currently uses a BD Insyte Autoguard 1.88in 18-gauge needle with self-retraction. Our protocol will not allow for attempting any vessel greater than 1.6cm from the skin surface for placement. The UGPIV will be placed with a Tegaderm over the probe for cleanliness. We will use sterile gel applied to the skin after a target vessel is identified. Once the vein is identified standard hospital gloves will be worn for safety and to avoid infection. Once the target vessel is identified an ultrasound image of the vessel will be captured and recorded with the patient's study ID number to allow for vessel depth and size to be measured. For both UGPIV and midline placement, operators will be instructed to attempt placement with short-axis out-of-plane technique, visualize the "vanishing target sign," and confirm catheter placement once deployed with long-axis in-plane view.¹⁰

BARD Powerglide Pro Midline: Boston Medical Center is currently approved and using an 18-gauge midline catheter. This midline catheter is unique in that it is a standard 10cm and does not require premeasurement or trimming of the catheter prior to placement. The physician will have measured from the axillary vein to the target needle entry location to ensure the catheter does not enter into the axillary vein. Additionally, because it is only 10cm it does not require a

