confirmatory chest x-ray or EKG waveform confirmation prior to usage. The physician will wear sterile gloves, gown, mask, and cap. The patient will be prepped with chlorhexidine, and as with the UGPIV, a tourniquet will be applied to the arm to increase the vessel size. The patient will be covered with a sterile drape that comes in the midline bundle set. A sterile probe cover will be applied to the ultrasound probe and be placed onto the sterile drape. Once the target vessel is identified, an ultrasound image of the vessel will be captured and recorded with the patient's study ID number from the randomization packet to allow for vessel depth and size to be measured. The vessel will then be selected and the needle will be guided by ultrasound until venous flash is obtained. The guidewire will be advanced and then using a seldinger technique the catheter advanced into the vessel. The catheter placement will then be confirmed with a long axis view of the catheter in the vessel. The catheter will then be secured in place and a Tegaderm will be placed over the entire midline insertion site to prevent infection.

BD Insyte Autoguard will be purchased by the hospital as already done without any changes in protocol. If patients are randomized to the UGPIV arm, they will be treated as receiving standard of care and will be billed as would otherwise be the case. These devices will be stored as already done within locked drawers in the IV carts in the emergency department.

BARD Powerglide Pro Midline; Bard will supply the training devices free of charge. This will include each provider placing 5 midline catheters for training purposes on phantom models. If patients are randomized they will not be charged for the MC placement. It is already hospital operating procedures not to bill for this procedure. MC will be stored in the charge nurse office to avoid them being stolen or used for non-study patients.

Both study groups will be responsible for any complications that occur. Because MC and UGPIV are already placed for clinical care the number of complications that are expected are low as they are considered already a safe and acceptable form of patient care.

Patients will also complete a few questions as a part of a survey to determine patient preferences with each device. The survey will be administered by physicians at the time of placement.

9 Study Procedures

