We additionally will capture the time spent placing each UGPIV in comparison to midline catheters. This will be accomplished by using the timestamp on the ultrasound at time of vessel identification, and then again at time of successful documentation of the catheter within the vessel. We will estimate for each failure of IV access a four-hour delay to have it replaced once hospitalized. Based on geographic cost, it is about \$100 per hour for inpatient hospitalization in Massachusetts. We additionally estimate the cost for staffing to be \$100 to replace a midline or UGPIV. We anticipate approximately a 5% failure in the midline group and 40% failure in the UGPIV group. We anticipate all midline failures will require repeat midline or CVC placement. We anticipate 10% of UGPIV will go on to get a CVC due to medical needs. We additionally estimate 33% of patients in the UGPIV group will require replacement during hospitalization. We anticipate one patient in the UGPIV to get a CVC and have a complication. CVC complications are reported to cost \$15,000 to \$50,000, however we will estimate a \$30,000 cost for each complication (example pneumothorax or line infection).¹²

Cost Estimate for 54 patients in UGPIV group:

54 initial UGPIV placements (54 x \$371): Projected outcomes: 5 patients progress to needing CVC (5 x \$1338), 17 subsequent failures getting repeat UGPIV (17 x \$371), 22 total failures at \$500 in estimated cost from delays in care and staffing (22 x \$500), 18 patients require additional access past 72-hour dwell time limit and get repeat UGPIV (18 x \$371). One CVC complication in the group of 54 patients: (1 x 30,000). = **Total Estimate: \$80,709**

Cost Estimate for 54 patients in Midline group:

54 initial midline placements (54 x \$1338), 3 failures with replacement cost and staffing and hospital delays (3 x \$1338 & 3 x 500), No complications expected or need for CVC. **Total Estimate: \$77,766**

We have projected a slight decrease in cost for midline placement at \$77,766 vs \$80,807 for 54 patients in this study. Based on these values with a power of 0.8 and alpha of 0.05 using a two

tailed t-test for independent means to predict a sample size with a SD of \$3,000 we will need to enroll 34 patients to adequately power our cost comparison group.

Aim 3: We will compare patient survey responses based on descriptive statistics, chi-square tests, or t tests as appropriate.

13 Ethics/Protection of Human Subjects

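### The placement-time clock starts at the vessel image, so as written it leaves out more preparation in the midline arm than in the UGPIV arm and tilts the Aim 2 time comparison towards the midline

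*Combined protocol and SAP*

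**What the plan says.** The Direct Cost Analysis part of Section 12.3 states the aim: "We additionally will capture the time spent placing each UGPIV in comparison to midline catheters". The clock starts from an image, "using the timestamp on the ultrasound at time of vessel identification". It stops at a second image, which the plan describes as "and then again at time of successful documentation of the catheter within the vessel". No other start is defined for this duration. Section 4.1 lists placement time among the data to be collected for Aim 2.

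Section 8, Study Intervention, describes the two procedures. For the midline, the text runs in this order:

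- Operator: "The physician will wear sterile gloves, gown, mask, and cap"
- Skin: "The patient will be prepped with chlorhexidine", with a tourniquet
- Field: a sterile drape over the patient
- Probe: "A sterile probe cover will be applied to the ultrasound probe and be placed onto the sterile drape"
- Vessel image, described last: "Once the target vessel is identified, an ultrasound image of the vessel will be captured and recorded", labelled with the study ID from the randomization packet

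For the UGPIV, the text mentions a Tegaderm on the probe, then "We will use sterile gel applied to the skin after a target vessel is identified", then standard gloves, then the captured vessel image. It describes no gown, drape or sterile probe cover.

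**The concern.** Sterile set-up is the largest preparation difference that Section 8 describes between the two devices. A clock that starts at the vessel image does not see it if that image is taken after draping. The result would be presented as time spent placing the device, but it would cover only the part after preparation.

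The error is systematic and tied to the arm, so neither randomization nor a larger sample removes it. It also runs in the direction of the Aim 2 hypothesis, which expects midlines to be cost effective. Set-up time that is not recorded at the bedside probably cannot be recovered later.

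**Working it through.** **1. What the clock records.** For each arm, let S be the preparation time before the vessel image and R the time from vessel image to catheter image. Total placement time is S + R; the plan records R.

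- True difference, midline minus UGPIV: (S_M + R_M) − (S_U + R_U)
- Recorded difference: R_M − R_U
- Error, recorded minus true: −(S_M − S_U)

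The recorded comparison favours the midline whenever S_M exceeds S_U, by exactly that net difference.

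**2. What falls in S, taking the order of Section 8 as chronological in both arms.**

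| | Before the vessel image |
|---|---|
| Midline | sterile gloves, gown, mask, cap; chlorhexidine; tourniquet; drape; sterile probe cover |
| UGPIV | Tegaderm on probe; gel; ordinary gloves |

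Both arms lose some preparation. The midline loses much more, so S_M > S_U and the direction is settled on this reading.

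**3. Size in time.** The documents give no set-up minutes. With an assumed net difference S_M − S_U of 5, 10 or 15 minutes over 54 midline placements:

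- 54 × 5 / 60 = 4.5 h
- 54 × 10 / 60 = 9 h
- 54 × 15 / 60 = 13.5 h

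**4. The plan's cost projection.** Reproduced from Section 12.3:

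- UGPIV: 54 × 371 + 5 × 1338 + 17 × 371 + 22 × 500 + 18 × 371 + 30,000 = 20,034 + 6,690 + 6,307 + 11,000 + 6,678 + 30,000 = $80,709
- Midline: 54 × 1338 + 3 × 1338 + 3 × 500 = 72,252 + 4,014 + 1,500 = $77,766
- Gap: 80,709 − 77,766 = $2,943 in favour of the midline

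Both totals reproduce exactly. No term contains placement minutes, so the clock does not enter them.

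**5. If a labour cost were later built from this clock.** The projection has 54 + 3 = 57 midline placements, so uncounted labour of 2,943 / 57 = $51.63 per placement would close the gap. With net set-up of m minutes and a rate of r dollars per hour, the amount is 57 × m/60 × r:

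| m (assumed) | r (assumed) | Uncounted | Remaining gap |
|---|---|---|---|
| 5 min | $50/h | $237.50 | $2,705.50 |
| 10 min | $100/h | $950 | $1,993 |
| 15 min | $200/h | $2,850 | $93 |
| 20 min | $200/h | $3,800 | −$857 |

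The minutes and rates are assumptions. The plan's own $100 per hour is a hospitalization cost, not an operator rate. The table also assumes that set-up labour is not already inside the $1338 unit price, which the documents do not say.

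**The case against.** **Both clocks may run over the same interval.** A reader might infer that the arms are timed from different points, with UGPIV gel and gloves inside the clock and midline set-up outside it, so that the whole error sits in one arm. The text does not support this. Section 8 puts the saved UGPIV image after the Tegaderm, gel and gloves, just as it puts the midline image after draping. Starting the UGPIV clock at first sight of the vein, but the midline clock at the saved image, mixes two readings. This part of the objection stands: preparation is lost in both arms, and only the net difference matters.

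**The midline image may be saved earlier.** Eligibility under Section 7.2 depends on vessel depth, and Section 8 has the physician measure from the axillary vein to the entry site, so an earlier look at the vessel is implied. The order of sentences is weak evidence of timing. This stands as doubt about practice. However, the only midline vessel image that Section 8 describes carries the packet's study ID and comes after the probe cover. If operators differ, the start point is inconsistent, which also calls for a definition.

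**Midline labour cost is not shown to be understated.** A reader might infer that it is. The plan has no rule for turning placement minutes into dollars. The $371 and $1338 unit prices and the $100 staffing charge per replacement are fixed, and the staffing charge is the same for both devices. This stands.

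**Image-to-catheter time is a legitimate measure.** It is objective and worth keeping. It is cannulation time, though, and the plan presents it as the time spent placing the device.

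**Conclusion.** The point holds for the placement-time comparison. As Section 8 is written, the interval in Section 12.3 omits preparation in both arms and considerably more in the midline arm, so it favours the midline. If image timing differs between operators, there is also an undefined start point.

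The direction rests on taking the order of Section 8 as the order of the procedure. The size cannot be derived from the documents; 4.5 to 13.5 operator hours over 54 placements rests on an assumed net 5 to 15 minutes.

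The consequences are limited. The projected totals of $80,709 and $77,766 stand. Only a labour cost later computed from this clock would be too low for the midline. The primary outcome is unaffected, because catheter survival is counted from placement and does not use this interval. The change is worth making because the measure is a stated Aim 2 item and the remedy is small.

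**What to change.** In both arms, save a time-stamped ultrasound image, or record a time, when the target vessel is first located and before any gowning or skin preparation. Define total placement time as running from that point to the image confirming the catheter in the vessel. Keep the existing interval from vessel image to catheter image and report it separately as cannulation time.

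Packet opening is a weaker common start. Section 8 stores midlines in the charge nurse office and UGPIVs in the emergency department IV carts, so retrieval time would be added mainly to the midline arm. For the same reason, the start image is best taken with the assigned device already at the bedside.

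If placement time is to enter the cost analysis, the plan should also state the rate used and whether the unit prices already include operator time.

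The cost is one extra image or time entry per placement and a few lines in Sections 8 and 12.3.

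### The UGPIV cost total is itemised as $80,709 but compared as $80,807, and the cost sample size of 34 becomes 36 by the plan's stated t-test once the itemised total is used

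*Combined protocol and SAP*

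**What the plan says.** Section 12.3 projects the cost of each arm for 54 patients. Under "Cost Estimate for 54 patients in UGPIV group" it lists six components and prints a total of $80,709. For the midline arm it lists initial placements and three failures and prints $77,766.

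The paragraph after the itemisations reads "We have projected a slight decrease in cost for midline placement at" $77,766, with $80,807 as the UGPIV comparator. From those values, an SD of $3,000, alpha 0.05, power 0.8 and a two-tailed t-test for independent means, it derives a requirement of 34 patients.

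On staffing, the text says "We additionally estimate the cost for staffing to be" $100 for replacing either device. This comes just after a four-hour delay assigned to each access failure and an hourly inpatient cost of $100. In the itemisation, staffing appears in "22 total failures at \$500 in estimated cost from delays in care and staffing (22 x \$500" and in the $500 attached to each of the three midline failures. The line "18 patients require additional access past 72-hour dwell time limit and get repeat UGPIV" is costed at $371 each, with no staffing term.

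**The concern.** One quantity has two values in adjoining paragraphs, and the value used downstream is not the one supported by the listed lines. The projected saving and the cost sample size both depend on it. Cost is Aim 2 of the trial, so a reader who rebuilds the calculation from the itemised lines with the named test will not reach the printed 34.

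The staffing text raises a smaller question. The plan does not say whether the $100 applies when a UGPIV is replaced for a reason other than failure. If this is left open, the rule for the observed data could be chosen after the data are seen.

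**Working it through.** All inputs are from section 12.3, Direct Cost Analysis.

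**1. UGPIV total**

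| Line | Amount |
|---|---|
| Initial placements, 54 x $371 | $20,034 |
| Progress to central venous catheter (CVC), 5 x $1,338 | $6,690 |
| Repeat UGPIV after failure, 17 x $371 | $6,307 |
| Delay and staffing, 22 x $500 | $11,000 |
| Repeat UGPIV past 72 hours, 18 x $371 | $6,678 |
| CVC complication, 1 x $30,000 | $30,000 |
| **Sum** | **$80,709** |

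This equals the printed itemised total.

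**2. Midline total.** 54 x $1,338 + 3 x $1,338 + 3 x $500 = 72,252 + 4,014 + 1,500 = $77,766, as printed.

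**3. The discrepancy.** 80,807 - 80,709 = $98. All the listed lines together come to less than $80,807, so no selection of them can reach it. Nor is the $98 a staffing term, because it is smaller than a single $100 charge.

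**4. The plan's sample size, reproduced.** Difference 80,807 - 77,766 = $3,041; standardised difference 3,041 / 3,000 = 1.014. A two-sided two-sample t-test (1:1, alpha 0.05, power 0.80, noncentral t) gives n = 16.30, so 17 per arm and 34 in total. This matches the plan. Power at 17 per arm is 81.7%.

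**5. The same calculation with the itemised total.** Difference 80,709 - 77,766 = $2,943; standardised difference 2,943 / 3,000 = 0.981. The t-test gives n = 17.33, so 18 per arm and 36 in total. Power at 17 per arm is 79.2%.

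**6. Cross-check by normal approximation.** n per arm = 2 x (1.960 + 0.842)² / d², or about 15.70 / d². For d = 1.014 this rounds up to 16 per arm (32 in total); for d = 0.981 it rounds up to 17 per arm (34 in total).

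**7. The staffing clarification.** The $500 per failure is 4 hours x $100 plus $100 staffing. If the $100 were also charged on the 18 replacements past 72 hours, it would add 18 x $100 = $1,800. The UGPIV total would be 80,709 + 1,800 = $82,509 and the difference 82,509 - 77,766 = $4,743. The standardised difference is then 1.581 and the t-test gives n = 7.38, so 8 per arm and 16 in total.

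**The case against.** **The error is close to a typing slip.** $98 is 0.12% of the UGPIV total (98 / 80,709) and about 3% of the projected saving (98 / 2,943). The midline still comes out cheaper, the requirement moves by two patients, and sections 2 and 12.2 already plan at least 54 per arm. All of this stands, and it limits the point to a correction of figures.

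**The 34 might not come from $80,807.** By step 6, the itemised total with a normal approximation also gives 34, so how the sponsor reached that number cannot be proved. However, the text names a t-test and says that it works from the values just quoted. As written, the 34 follows from $80,807. The itemised total with the named test gives 36.

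**A reader might infer that both totals are also wrong for omitting $1,800 of staffing.** In favour of that reading, the staffing sentence has no explicit limit to failures, the plan elsewhere describes a third of UGPIV patients as needing replacement, and the repeat UGPIVs after failure carry staffing on top of the $371. The documents do not establish it. The staffing sentence follows directly on the per-failure delay, and the itemisation charges staffing only inside the $500 per failure, in both arms. Read as a per-failure cost, the charge is applied consistently and $80,709 is right. Charging it more widely would increase the projected midline saving, so the present figures do not favour the plan's hypothesis on this point.

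**Conclusion.** The inconsistency is established: $80,807 should read $80,709 by the plan's own lines, the projected saving is $2,943 instead of $3,041, and the stated t-test then requires 36 patients instead of 34. This rests on the plan's SD, alpha, power and equal allocation, and on reading 34 as the total for two arms, which is the reading that reproduces it.

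The importance is minor. Planned enrolment exceeds either figure, so a reader should not infer that recruitment or power for the primary aim is affected.

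Nor should a reader infer that 36 makes the cost comparison adequately powered. The calculation sets a difference between two 54-patient totals against an SD whose unit is not stated. If the SD is per patient, which is an assumption, the itemised difference is 2,943 / 54 = $54.50 per patient, and the normal approximation gives 47,565 per arm. That is a separate and larger question, which correcting the total does not resolve.

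The staffing rule is ambiguous and needs one sentence. It is not a demonstrated error.

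**What to change.** In section 12.3, replace $80,807 with $80,709, quote the difference as $2,943, and restate the cost sample size as 36 (18 per arm) by the plan's own t-test. Correcting the total while leaving the 34 in place would still leave a number that does not match its inputs.

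Add one sentence saying whether the $100 staffing charge applies to every replacement or only to failures, and apply the same rule to the observed data. If only to failures, the figures above stand. If to every replacement, restate the chain together: UGPIV $82,509, difference $4,743, and 8 per arm (16 in total) by the same method.

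The cost is three corrected figures and one sentence, with no change to enrolment or conduct.

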4.1 Study Objectives

Aim 1: To determine if UGPIVs have a higher failure rate than midline catheters within 72 hours of placement.

There are several reasons why UGPIVs may fail. UGPIVs are shorter than midline catheters, and shorter catheters may fail due to infiltration which can be a result of malposition as well as having the catheter pull out of the vessel. We suspect that by using a midline catheter with a guidewire for placement with additional catheter length placed into the vessel, midlines will be superior to UGPIVs with regards to survival time of the catheter.

Hypothesis: Midline catheters have a lower failure rate at 72-hours compared to ultrasound guided peripheral IVs.

Aim 2: To perform a direct cost analysis of UGPIV against that of the midline catheter.

This study will not be large enough to complete a robust cost effectiveness analysis to compare UGPIV to midline catheters. As a part of this study we will collect information including but not limited to: the number of catheters used for IVA attempts, time for placement of each device, complications, and need for additional IV access during hospitalization (MC, PIV, or CVC).

Hypothesis: Midline catheters are a cost effective change in clinical practice due to lower complication rate and longer dwell times.

Aim 3: To determine patient experience and satisfaction with each device to determine patient preference.

Our goal will be to compare UGPIV to MC for patient experience (including pain, satisfaction, and preference) based on survey.

Hypothesis: Pain scores will be similar between the UGPIV and MC group, however patients will prefer the placement of the MC.

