12.1 Study Hypotheses

The primary hypothesis is that midline catheters will be superior to ultrasound guided IVs with relation to survival time.

Secondary assessment will 1) attempt to prove that MC are superior to UGPIV with relation to cost effectiveness despite their overall higher upfront cost. 2) Patients will experience similar pain between MC and UGPIV, however will prefer the MC knowing the survival of the catheter is longer.

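### The 34-patient power claim for the cost comparison treats a difference between 54-patient totals as a per-patient difference; power for the projected saving is about 5%

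*Combined protocol and SAP*

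**What the plan says.** Section 12.3 builds one cost estimate per arm. The headings are "Cost Estimate for 54 patients in UGPIV group" and "Cost Estimate for 54 patients in Midline group", and each figure is a sum of counts times unit costs over the whole arm. The itemised UGPIV estimate is given as $80,709 and the midline estimate as $77,766. The text then states: "We have projected a slight decrease in cost for midline placement at \$77,766 vs \$80,807 for 54 patients in this study". The sample size follows directly from these totals: "Based on these values with a power of 0.8 and alpha of 0.05 using a two"-tailed t-test for independent means and an SD of $3,000, the plan concludes that "we will need to enroll 34 patients to adequately power our cost comparison group". It gives no per-patient mean or difference, no unit or source for the SD, and does not say whether 34 is per arm or in total.

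Two other places bear on the claim. Section 12.1 says the secondary assessment will "attempt to prove that MC are superior to UGPIV with relation to cost effectiveness despite their overall higher upfront cost". Section 4.1, under Aim 2, says "This study will not be large enough to complete a robust cost effectiveness analysis".

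**The concern.** A two-sample t-test on patients needs a difference in mean cost per patient and an SD of cost per patient. The plan supplies totals for 54 patients, and nothing in the text divides them by 54. If the difference in totals went into the formula unchanged, the effect size is 54 times too large and the required sample size too small by a factor of about 54² = 2,916.

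A reader who accepts the statement will think that 108 patients are ample for Aim 2, since only 34 are said to be needed. A non-significant cost comparison could then be taken as evidence that the devices cost the same, although the trial could not have detected the saving it projects.

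**Working it through.** **Inputs, all from Section 12.3 (arm size also in Section 12.2).** Group totals $77,766 and $80,807 (or $80,709 itemised); SD $3,000; two-sided alpha 0.05; power 0.80; 54 patients per arm.

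**1. Check the totals.**
- UGPIV: 54×371 + 5×1,338 + 17×371 + 22×500 + 18×371 + 30,000 = 20,034 + 6,690 + 6,307 + 11,000 + 6,678 + 30,000 = $80,709.
- Midline: 54×1,338 + 3×1,338 + 3×500 = 72,252 + 4,014 + 1,500 = $77,766.

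So $80,709 is right and the later $80,807 is $98 too high. The difference in totals is $3,041 as the plan compares them, or $2,943 from the itemised figures.

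**2. Reproduce the 34.** Enter $3,041 as if it were a difference in patient means: d = 3,041/3,000 = 1.01. The normal approximation, n per arm = 2(1.96 + 0.8416)²/d², gives 15.3, rounded up to 16. The t-test (noncentral t) gives 16.3, rounded up to 17 per arm, so 34 in total. This matches the plan exactly. With $2,943 the t-test gives 18 per arm, 36 in total.

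**3. Put the difference on the patient scale.**
- UGPIV: 80,709/54 = $1,494.61. Midline: 77,766/54 = $1,440.11. Difference: 2,943/54 = $54.50, so d = 54.50/3,000 = 0.018.
- Using $80,807: 3,041/54 = $56.31, so d = 0.019.

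**4. Power and sample size on that scale (SD $3,000 per patient, two-sided t-test).**

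| Patients per arm | Power, difference $54.50 | Power, difference $56.31 |
|---|---|---|
| 17 (34 in total) | 5.03% | 5.03% |
| 34 (34 read as per arm) | 5.06% | 5.07% |
| 54 (planned) | 5.10% | 5.11% |

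For 80% power, n per arm = 2(1.96 + 0.8416)²×(3,000/54.50)² ≈ 47,565 by the normal approximation and about 47,570 by the t-test. With $56.31 the figures are 44,549 and about 44,550.

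**5. Precision at 54 per arm.** The standard error of the difference is 3,000×√(2/54) = $577. The 95% CI half-width is 1.96×577 ≈ $1,130 (about $1,145 with the t quantile), some 20 times the projected saving. The difference detectable with 80% power is 2.80×577 ≈ $1,617 (about $1,632 by the t-test).

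**6. Vary the SD, because its unit is not stated.**
- If $3,000 is the SD of a 54-patient total, the per-patient SD is 3,000/√54 = $408. With a difference of $56.31, power is about 7% at 17 per arm, 9% at 34 and 11% at 54, and about 825 per arm would be needed.
- For an assumed per-patient SD from $500 to $5,000, power at 17 to 54 per arm runs from 5.0% to 8.9%.
- Spreading the plan's cost items over individual patients gives an SD of about $4,288 for UGPIV and $425 for midline, pooled about $3,050. The plan does not say how events fall on patients. This assumes that the 5 CVC patients and the 17 with a repeat UGPIV are different people, that 18 of the remaining 32 need later access, and that one CVC patient has the complication. The single $30,000 event dominates the UGPIV SD. On this basis $3,000 is credible as a per-patient SD, and power remains about 5%.

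**7. What the projected saving rests on.** Without the $30,000 complication the UGPIV total is $50,709, or $939 per patient, against $1,440 for midline. At $15,000, the low end of the range the plan quotes, the UGPIV total is $65,709, still below $77,766. The saving disappears once the complication costs less than 30,000 − 2,943 = $27,057.

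**The case against.** The strongest defence is that the 34 drives nothing. Enrolment is set by Aim 1 at 54 per arm, cost is a secondary aim, and the t-test is named here only to predict a sample size. Section 4.1 already warns that the study is too small for a robust cost-effectiveness analysis, and Section 12.3 puts a complete one out of scope. These warnings concern cost-effectiveness whereas the 34 concerns direct cost, so this is a tension between sections and not a strict contradiction. Section 12.1 speaks of an attempt to prove superiority, not of a promised result. No equivalence conclusion is planned, and true costs could differ by far more than projected, so a significant result need not be spurious. The $98 discrepancy moves the sample size by only two patients. The figure of about 5% depends on reading the SD as per patient.

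Most of this is fair and limits the consequences. None of it makes the 34 correct. No section converts the totals to a per-patient scale, and no reading of the SD or of 34 as per arm brings power near 80%. The general caveats do not withdraw a specific statement that the cost comparison is adequately powered.

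**Conclusion.** The concern holds. The 34 comes from a unit error: group totals were used where per-patient means were required. For the plan's own projected saving, power is about 5% with 34 patients and with the full 108, taking $3,000 as a per-patient SD. The most favourable reading of the SD examined, as that of a group total, raises it to at most about 11%. The conclusion rests on the plan's projected costs and on the comparison being made between individual patients, as an independent-means t-test requires. The UGPIV total of $80,807 is a separate, minor error. The primary sample size is unaffected.

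**What to change.** In Section 12.3, delete the 34-patient statement and say plainly that the trial is not powered for cost. Plan to report mean cost per patient in each arm and the difference with a 95% confidence interval, labelled descriptive. A bootstrap interval suits costs this skewed, though the method is a choice. If the projections stay, give them per patient ($1,494.61 for UGPIV, $1,440.11 for midline), correct $80,807 to $80,709, and note that the direction of the difference depends on one assumed complication. In Section 12.1, replace the aim of proving superiority with one of estimating the cost difference, which also brings it into line with Section 4.1.

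The cost is wording only. A claimed power is withdrawn; enrolment, data collection and the primary analysis stay as they are.
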